7.0 REGULATORY AND REPORTING REQUIREMENTS

The entities providing oversight of safety and compliance with the protocol require reporting as outline below.

The Washington University Human Research Protection Office (HRPO) requires that all events meeting the definition of unanticipated problem or serious noncompliance be reported as outlined in Section 7.2.

Novartis requires that all events be reported as outlined in Section 7.4.

7.1 Definitions

7.1.1 Adverse Events (AEs)

Definition: any unfavorable medical occurrence in a human subject including any abnormal sign, symptom, or disease.

Grading: the descriptions and grading scales found in the revised NCI Common Terminology Criteria for Adverse Events (CTCAE) version 4.0 will be utilized for all toxicity reporting. A copy of the CTCAE version 4.0 can be downloaded from the CTEP website.

Attribution (relatedness), Expectedness, and Seriousness: the definitions for the terms listed that should be used are those provided by the Department of Health and Human Services' Office for Human Research Protections (OHRP). A copy of this guidance can be found on OHRP's website:

<http://www.hhs.gov/ohrp/policy/advevntguid.html>

7.1.2 Serious Adverse Event (SAE)

Definition: any adverse drug experience occurring at any dose that results in any of the following outcomes:

- Death

- A life-threatening adverse drug experience
- Inpatient hospitalization or prolongation of existing hospitalization
- A persistent or significant disability/incapacity (i.e., a substantial disruption of a person’s ability to conduct normal life functions)
- A congenital anomaly/birth defect
- Any other experience which, based upon appropriate medical judgment, may jeopardize the subject and may require medical or surgical intervention to prevent one of the outcomes listed above

7.1.3 Unexpected Adverse Experience

Definition: any adverse drug experience, the specificity or severity of which is not consistent with the current investigator brochure (or risk information, if an IB is not required or available).

7.1.4 Life-Threatening Adverse Experience

Definition: any adverse drug experience that places the subject (in the view of the investigator) at immediate risk of death from the reaction as it occurred, i.e., it does not include a reaction that, had it occurred in a more severe form, might have caused death.

7.1.5 Unanticipated Problems

Definition:

- unexpected (in terms of nature, severity, or frequency) given (a) the research procedures that are described in the protocol-related documents, such as the IRB-approved research protocol and informed consent document; and (b) the characteristics of the subject population being studied;
- related or possibly related to participation in the research (“possibly related” means there is a reasonable possibility that the incident, experience, or outcome may have been caused by the procedures involved in the research); and
- suggests that the research places subjects or others at a greater risk of harm (including physical, psychological, economic, or social harm) than was previously known or recognized.

7.1.6 Noncompliance

Definition: failure to follow any applicable regulation or institutional policies that govern human subjects research or failure to follow the determinations of the

IRB. Noncompliance may occur due to lack of knowledge or due to deliberate choice to ignore regulations, institutional policies, or determinations of the IRB.

7.1.7 Serious Noncompliance

Definition: noncompliance that materially increases risks, that results in substantial harm to subjects or others, or that materially compromises the rights or welfare of participants.

7.1.8 Protocol Exceptions

Definition: A planned deviation from the approved protocol that are under the research team's control. Exceptions apply only to a single participant or a singular situation.

Pre-approval of all protocol exceptions must be obtained prior to the event.

7.2 Reporting to the Human Research Protection Office (HRPO) at Washington University

The PI is required to promptly notify the IRB of the following events:

- Any unanticipated problems involving risks to participants or others which occur at WU, any BJH or SLCH institution, or that impacts participants or the conduct of the study.
- Noncompliance with federal regulations or the requirements or determinations of the IRB.
- Receipt of new information that may impact the willingness of participants to participate or continue participation in the research study.

These events must be reported to the IRB within **10 working days** of the occurrence of the event or notification to the PI of the event. The death of a research participant that qualifies as a reportable event should be reported within **1 working day** of the occurrence of the event or notification to the PI of the event.

7.3 Reporting to the Quality Assurance and Safety Monitoring Committee (QASMC) at Washington University

The PI is required to notify the QASMC of any unanticipated problem occurring at WU or any BJH or SLCH institution that has been reported to and acknowledged by HRPO as reportable. (Unanticipated problems reported to HRPO and withdrawn during the review process need not be reported to QASMC.)

QASMC must be notified within **10 days** of receipt of IRB acknowledgment via email to a QASMC auditor.

7.4 Reporting to Novartis

All events must be reported to Novartis within 24 hours of learning of its occurrence. Information about all SAEs is collected and recorded on a Serious Adverse Event Report Form; all applicable sections of the form must be completed in order to provide a clinically thorough report. The investigator must assess and record the relationship of each SAE to each specific study treatment (if there is more than one study treatment), complete the SAE Report Form in English, and **send the completed, signed form by fax to ([contact]) within 24 hours to the oncology Novartis DS&E department with the provided FAX cover sheets.** (See Appendices E and F). This includes serious, related, labeled (expected) and serious, related, unlabeled (unexpected) adverse experiences. All deaths during treatment or within 30 days following completion of active protocol therapy must be reported within 5 working days.

From the time a subject consents to participate in and completes the study all SAEs assessed as related to study participation (e.g., protocol-mandated procedures, invasive tests, or change in existing therapy) or related to Novartis concomitant medication, will be reported promptly to Novartis.

Any SAE brought to the investigator's attention within 30 days following completion of the study considered by the investigator as possibly related to investigational product must be reported to Novartis. Recurrent episodes, complications, or progression of the initial SAE must be reported as follow-up to the original episode within 24 hours of the investigator receiving the follow-up information. A SAE occurring at a different time interval or otherwise considered completely unrelated to a previously reported one should be reported separately as a new event. The end date of the first event must be provided.

Follow-up information is sent to the same fax number as the original SAE Report Form was sent, using a new fax cover sheet, stating that this is a follow-up to the previously reported SAE, and giving the date of the original report. Each re-occurrence, complication, or progression of the original event should be reported as a follow-up to that event regardless of when it occurs. The follow-up information should describe whether the event has resolved or continues, if and how it was treated, whether the blind was broken or not (if applicable), and whether the patient continued or withdrew from study participation.

If the SAE is not previously documented in the Pazopanib Investigator Brochure or Package Insert (new occurrence) and is thought to be related to the Novartis study drug, a DS&E associate may urgently require further information from the investigator for Health Authority reporting. Novartis may need to issue an Investigator Notification (IN), to inform all investigators involved in any study with the same drug that this SAE has

been reported. Suspected Unexpected Serious Adverse Reactions (SUSARs) will be collected and reported to the competent authorities and relevant ethics committees in accordance with Directive 2001/20/EC or as per national regulatory requirements in participating countries.

Please note that all events meeting liver stopping criteria must be recorded as an SAE.

Pregnancy

Any pregnancy that occurs during study participation must be reported to Novartis. To ensure subject safety, each pregnancy must be reported to Novartis within 24 hours of learning of its occurrence using the pregnancy reporting form. The pregnancy must be followed up to determine outcome (including premature termination) and status of mother and child. Pregnancy complications and elective terminations for medical reasons must be reported as an AE or SAE. Spontaneous abortions must be reported as an SAE.

Any SAE occurring in association with a pregnancy brought to the investigator's attention after the subject has completed the study and considered by the investigator as possibly related to the investigational product, must be promptly reported to Novartis. In addition, the investigator must attempt to collect pregnancy information on any female partners of male study subjects who become pregnant while the subject is enrolled in the study. Pregnancy information must be reported to Novartis as described above.

All serious adverse events must be reported by facsimile within 24 hours to Novartis.

[contact]

Email: [contact]

Phone: [name], [contact] (if you experience difficulty faxing the form)

Please use the attached fax cover sheet, located in Appendices E and F.

	Initial Reports	Follow-up Information on a Previous Report
Type of Event	Time Frame	Documents
All SAEs	24 hours	For follow-up report, please submit findings from the previous report, if appropriate
Pregnancy	24 hours	
Liver Chemistry Abnormalities (the below are not always considered an SAE unless they fulfill the definition of an SAE in Section 7.7)		
ALT: >3.0 x ULN with concomitant elevation in bilirubin ^a (defined as total bilirubin ≥2.0 x ULN; with direct bilirubin >35%) or with hypersensitivity symptoms (e.g., fever, rash).	24 hours	For follow-up report, please submit findings from the previous report, if appropriate
ALT >8.0 x ULN without bilirubin elevation (defined as total bilirubin ^a <2.0 x ULN or direct bilirubin ≤35%) and without hypersensitivity symptoms (e.g., fever, rash)	24 hours	For follow-up report, please submit findings from the previous report, if appropriate

- a. Bilirubin fractionation should be performed if testing is available. If testing is unavailable and a subject meets the criterion of total bilirubin >1.5 x ULN, then the event should be promptly reported as an SAE.

7.5 Timeframe for Reporting Required Events

Reportable adverse events will be tracked for 30 days following the last day of study treatment.

8.0 PHARMACEUTICAL INFORMATION

8.1 Pazopanib

8.1.1 Pazopanib Description

GW786034 (pazopanib) is a vascular endothelial growth factor (VEGF) receptor tyrosine kinase inhibitor (TKI) being developed by Novartis for oncology indications (as an oral formulation) and for ophthalmology indications (eye drops and low dose oral). Pazopanib has been approved by the U.S. Food and Drug Administration (FDA) for the treatment of patients with advanced renal cell carcinoma (RCC) (New Drug Application [NDA] #022465).

Chemical Name: 5-[[4-[(2,3-Dimethyl-2H-indazol-6-yl)methylamino]-2-pyrimidinyl]amino]-2-methylbenzenesulfonamide monohydrochloride

Molecular Formula: C₂₁H₂₃N₇O₂S • HCl

Molecular Weight: 473.99 g/mol (monohydrochloride salt); 437.53 g/mol (free base)

8.1.2 Pharmacokinetics and Drug Metabolism

Pazopanib is absorbed orally with median time to achieve peak concentrations of 2 to 4 hours after the dose. Daily dosing at 800 mg results in geometric mean AUC and C_{max} of 1,037 mcg·hr/mL and 58.1 mcg/mL (equivalent to 132 µM), respectively.

8.1.3 Supplier(s)

Pazopanib will be provided to the sites by Novartis. Please use the ISS Drug Supply Request form (Appendix D) to order drug. Contact [name] ([contact]) and [name] ([contact]) and cc [name] ([contact]) on ALL requests.

8.1.4 Dosage Form and Preparation

Pazopanib is supplied as 200 mg tablets. Tablets are packaged in a sealed bottle with an affixed content label identifying the product.

8.1.5 Storage and Stability

Store at room temperature between 20°C and 25°C; excursions permitted to 15°C to 30°C.

8.1.6 Administration

Pazopanib at a dose of 800 mg QD (four 200 mg tablets) should be taken orally without food at least one hour before or two hours after a meal.

9.0 CORRELATIVE STUDIES

9.1 Tumor Tissue For Research Purposes

With patient consent, archived formalin fixed paraffin embedded specimens from the time of diagnosis may be sequenced as part of the patient's routine care. If archival tissue samples are available and/or biopsy is obtained for clinical purposes at the time of disease progression, WUSM may request a tumor sample, with patient consent, for research purposes, including whole exome and transcriptome sequencing. The specimens will be collected in accordance with standard of care practice and will be taken to the Washington University Tissue Procurement Core for processing and storage per institutional practice.

For the purpose of eligibility, patients expressing pazopanib targeted genes in either tissue assays or peripheral blood should be considered for study.

10.0 STUDY CALENDAR

Screening/baseline evaluations are to be conducted no more than 14 days prior to start of protocol therapy. Scans and x-rays must be done no more than 4 weeks prior to the start of the protocol therapy. All visits have a window of +/- 3 days.

	Screening	D1 of each cycle	C1D8	C1D15 and C2D15	End of every even-numbered cycle	EOT	F/U ⁹
Informed consent	X						
PE, H&P, PS	X	X				X	
VS	X	X ¹	X			X	
CBC	X	X	X			X	
CMP	X	X	X			X	
LFTs ²	X	X ²	X ²	X ²		X	
Pregnancy test ³	X					X	
UPC	X	X ¹⁰				X	
TSH, T4	X	X ⁴					
PT/PTT, INR	X					X	
ECG	X	X ⁵					
CT scan	X				X	X	
Pazopanib		X ----- X ⁶					
Collect/review medication diary		X					
Toxicity assessment	X	X				X ¹¹	
Tissue for Research Purposes	X ⁷					X ⁷	

1. **Monitoring of BP only at Day 7 +/- 3 days.** Can be assessed by any method as long as the study physician is informed of the measurement, verifies any measurement that is not normal, and takes appropriate action.

2. Monitor serum liver tests before initiation of treatment with pazopanib and C1D15, C2D1, C2D15, C3D1, C4D1, C5D1, and as clinically indicated. Periodic monitoring should continue after C5.

3. Women of childbearing potential only.

4. Monitor between every 8 to every 16 weeks.

5. C2D1, C4D1, C7D1 and then every 16 weeks (Day 1 of every fourth cycle) until EOT.

6. To be taken PO QD. Each cycle is 4 weeks long.

7. Optional tissue for research purposes per section 9.1.9. Patients will be followed every 2 months for recurrence and survival until death.

10. Day 1 of each cycle through Cycle 6, then Day 1 of every even-numbered cycle thereafter.

11. Last assessment to take place 30 days following end of treatment.

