6.0 DOSE DELAYS/DOSE MODIFICATIONS

As a general rule, if dose reduction of pazopanib is necessary, the dose should be reduced stepwise by 200 mg at each step, and the subject should be monitored for approximately 10 to 14 days at each dose level. If toxicity does not abate during this monitoring time, the pazopanib may need to be interrupted and/or the dose further decreased with continued monitoring for an additional 10-14 days at each dose level, and so on.

If the toxicity has abated with reduction of the dose and dose re-escalation is considered safe by the investigator, the pazopanib dose can then be increased step-wise back to the pre-event dose

(in 200 mg increments, after monitoring for 10-14 days at each dose level to ensure that toxicity did not recur or worsen).

Dose-level	0	-1	-2	-3	-4
Dose	800 mg QD	600 mg QD	400 mg QD	200 mg QD	Discontinue

For patients at dose-level -3, 200 mg QD, a maximum dose delay of 14 days is allowed for management of toxicities. If toxicity does not resolve in 14 days, the patient should be discontinued from study.

Dose Modification Algorithms for Potential Treatment-Related Adverse Events

AE Terms & Descriptions	Dose Modification Algorithms
Hypertension	
(A). Asymptomatic and persistent SBP of ≥ 140 - <170 mmHg, or DBP ≥ 90 - <110 mmHg, or a clinically significant increase in DBP of 20 mmHg (but still below 110 mmHg).	Step 1. Continue pazopanib at the current dose. Step 2. Adjust current or initiate new antihypertensive medication(s). Step 3. Titrate antihypertensive medication(s) during next 2 weeks as indicated to achieve well-controlled ^a blood pressure (BP). If BP is not well-controlled within 2 weeks, consider referral to a specialist and go to scenario (B).
(B). Asymptomatic SBP ≥ 170 mmHg, or DBP ≥ 110 mmHg, or failure to achieve well-controlled BP within 2 weeks in scenario (A).	Step 1. Consider reducing or interrupting pazopanib, as clinically indicated. Step 2. Adjust current or initiate new antihypertensive medication. Step 3. Titrate antihypertensive medication(s) during next 2 weeks as indicated to achieve well-controlled BP. Step 4. Once BP is well-controlled, restart pazopanib dose-reduced by 200 mg if it was interrupted.

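### Adding a blood pressure reading at the existing C1D15 and C2D15 contacts would cut the longest scheduled gap in cycles 1 and 2 from 22 or 28 days to 14 (a cheap safety improvement, not an error)

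*Combined protocol and SAP*

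**What the plan says.** In the Section 10.0 calendar the vital signs row is marked at screening, Day 1 of every cycle, C1D8 and end of treatment. The cell for C1D15 and C2D15 is blank. Footnote 1, attached to the Day 1 mark, reads "Monitoring of BP only at Day 7 +/- 3 days" and names no cycle. On method it is permissive: "Can be assessed by any method as long as the study physician is informed of the measurement". It also expects the physician to check any abnormal value and act on it.

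The Day 15 contacts exist because of liver tests. Footnote 2 reads: "Monitor serum liver tests before initiation of treatment with pazopanib and C1D15, C2D1, C2D15, C3D1, C4D1, C5D1, and as clinically indicated". The calendar's general tolerance is "All visits have a window of +/- 3 days".

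The hypertension table in Section 6.0 covers patients without symptoms. Scenario A begins "Asymptomatic and persistent SBP of" and leads to starting or adjusting antihypertensives while pazopanib continues. Scenario B covers asymptomatic values of at least 170 systolic or 110 diastolic, or failure to gain control under A. There, reducing or interrupting pazopanib is to be considered.

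**The concern.** Section 1.3 names hypertension as the grade 3 toxicity seen most often in the phase I study. Scenarios A and B call for action in patients who feel well, so the action depends on someone taking a reading. A patient without symptoms may not prompt an unscheduled one. If BP rises soon after a scheduled reading, the calendar does not require another for three weeks or more, yet the patient is already due for a blood test about halfway through that time. At stake is how promptly a known, treatable toxicity is found and managed in the first two cycles. Response rate, progression-free survival and the sample size are not affected.

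**Working it through.** **Inputs.** Cycle length is 28 days (Section 5.1). Scheduled BP times, footnote 1 and the 3-day windows come from Section 10.0. N = 20 comes from Section 14.2. The plan states no BP interval, so there is no figure of its own to reproduce.

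**Other sources of a reading.** During treatment, the physical examination and toxicity rows are marked on Day 1 only. I found no on-treatment BP scheduled in Section 5.2, Section 6.0 (before a raised value or a dose reduction), Section 13.0 or the medication diary.

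**Study days.** Study day = (cycle − 1) × 28 + cycle day. Each contact is allowed to move by 3 days on its own:

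- C1D8 = 8 (5 to 11)
- C1D15 = 15 (12 to 18)
- C2D1 = 29 (26 to 32)
- C2D7 = 35 (32 to 38)
- C2D15 = 43 (40 to 46)
- C3D1 = 57 (54 to 60)

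**Gaps as the calendar stands.**

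- After C1D8: 29 − 8 = 21 days (26 − 11 = 15 to 32 − 5 = 27).
- Cycle 2, Day 7 check in every cycle: 57 − 35 = 22 days (54 − 38 = 16 to 60 − 32 = 28).
- Cycle 2, Day 7 check in cycle 1 only: 57 − 29 = 28 days (54 − 32 = 22 to 60 − 26 = 34).
- If the footnote mark is misplaced and belongs to C1D8, the cycle 1 gap is 21 days, or 29 − 7 = 22 if the reading is taken on Day 7. The cycle 2 gap is then 28.

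A gap of at least 21 nominal days remains under each of these readings.

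**Gaps with BP at C1D15 and C2D15.**

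- Cycle 1: 15 − 8 = 7 days, then 29 − 15 = 14 (26 − 18 = 8 to 32 − 12 = 20).
- Cycle 2, Day 7 in every cycle: 6, then 43 − 35 = 8, then 57 − 43 = 14 days (54 − 46 = 8 to 60 − 40 = 20).
- Cycle 2, Day 7 in cycle 1 only: 43 − 29 = 14, then 57 − 43 = 14 days (8 to 20 each).

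**Why the footnote needs a sentence too.** Taken with full literalness, footnote 1 could mean that BP is read on Day 7 instead of Day 1. That is unlikely, because vital signs are marked on Day 1. Under it the present gaps would be 35 − 8 = 27 and 63 − 35 = 28 days. Day 15 readings alone would leave 35 − 15 = 20 and 63 − 43 = 20 days, not 14.

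**Who gains.** A rise that starts after the preceding scheduled reading and by Day 15 is seen on Day 15 instead of the next Day 1, which is 14 days sooner (8 to 20). The helped window is 15 − 8 = 7 days in cycle 1. In cycle 2 it is 43 − 35 = 8 days or 43 − 29 = 14 days, depending on footnote 1. Onsets at other times gain nothing.

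**Average gain.** This is 14 × p days per cycle, where p is the share of that cycle's onsets in the helped window. The documents give no onset timing, so the range is 0 (p = 0) to 14 (p = 1). For illustration only, onset spread evenly over a cycle gives 14 × 7/28 = 3.5 days in cycle 1, and 14 × 8/28 = 4.0 or 14 × 14/28 = 7.0 days in cycle 2.

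**The case against.** The protocol already has a BP plan with an early check at C1D8, and no section fixes a maximum interval. Preferring 14 days to 21 or 22 is a judgement. That stands, and it is why this is offered as an improvement.

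The benefit is unproven. If most rises begin in the first week, C1D8 catches them and C1D15 adds nothing. Section 1.3 gives no hypertension rate, so the number of patients helped among 20 is unknown. Scenario A requires persistence, so one raised reading may need repeating before it applies. Exclusion 12 also keeps out poorly controlled hypertension. All of this limits the size of the gain; none of it supplies a mid-cycle reading.

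The 28-day figure rests on the less natural reading of footnote 1. A cycle 1 check on days 4 to 10 would nearly duplicate C1D8 on days 5 to 11, so the footnote adds most if it recurs, which gives 22 days. This is fair, and the point does not depend on the 28.

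The remedy also stops at cycle 2, although treatment may go on much longer. That stands as a limit: the restriction follows the existing paired contacts, not evidence that later risk is lower.

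A reader might infer that the calendar contradicts Section 6.0, where the instruction is "Titrate antihypertensive medication(s) during next 2 weeks as indicated". It does not. Titration starts once raised BP is known and implies its own extra readings. The same goes for the general rule that "the subject should be monitored for approximately 10 to 14 days at each dose level", which follows a dose reduction. Only first detection is in question.

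**Conclusion.** The point holds as a low-cost safety improvement, not as an error. Scheduled first detection of asymptomatic hypertension has a 21-day gap after C1D8 (15 to 27), and in cycle 2 a gap of 22 days (16 to 28) or 28 days (22 to 34), depending on footnote 1. Two liver-test contacts fall inside those gaps unused. Using them brings the longest scheduled gap in cycles 1 and 2 to 14 days (8 to 20), provided the Day 7 check does not replace Day 1 vital signs.

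Two further inferences go too far. One is that patients go unmeasured for up to four weeks: these are scheduled gaps, unscheduled readings are not ruled out, and Section 13.0 asks for continuing attention to serious toxicity. The other is that hypertension would be found two weeks sooner in general. The 14 days applies only to onsets in the helped window, and assumes that the Day 15 reading picks up the rise.

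**What to change.** - In the vital signs row, mark a BP-only reading at C1D15 and C2D15, by any method footnote 1 accepts. This works even if Day 15 is only a laboratory draw.
- In footnote 1, state which cycles the Day 7 check covers and that it is additional to Day 1 vital signs.

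The cost is one calendar edit and one clarified footnote. There are at most 2 further readings per patient, 2 × 20 = 40 in all, with their data entry. The study physician must also verify and act on any abnormal value, as footnote 1 already requires, and some values may need a repeat. No visit, threshold or treatment rule is added. The 22- or 28-day gap from cycle 3 onward is unchanged; whether to add a mid-cycle reading there is for the sponsor to decide.
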